12.13 Sample Size and Power. Total potential sample size 240 (up to 120 per arm), to ensure at least 75 per arm completing the study with complete baseline COH-QOL-CRC scaled items, assuming a 15% dropout rate. This will maintain sufficient power for the COH-QOL-CRC scaled items. The larger sample size for the primary endpoints Patient Activation Measure (PAM) and ostomy management self-efficacy (SE) will provide 80% power to detect a 2.75 change in PAM and a 0.50 change in SE, which is not considered excessively powered. Detectable differences based on variances observed from our R21 for PAM and SE, as well as from our R01 for COH-QOL-CRC subscales. We changed two items slightly on the self-efficacy questions to make them ostomy-relevant. Our observed variation for ostomy management SE is consistent with the original form of symptom management SE across different patient samples reported by Lorig's group (SD range 2.1 to 2.4).⁵¹⁻⁵⁷ We will examine the reliability of these items and expect them to have a Cronbach's alpha of ≥ 0.75 . Calculated detectable differences were based on the following assumptions 1) alpha of 0.05, 2) within-subject correlation on repeated measures of 0.60. Estimates are based on repeated measures multivariable modeling, adjusted for baseline,

with two follow-up measurements. Also shown for comparison are two rough indices of clinically important differences. Sufficient research has not been performed on these scales to determine with certainty a minimal clinically-important difference that is anchored on participant self-assessment of health status. An alternative suggested by Sloan⁵⁸ is the empirical rule effect size (ERES) method to judge minimally important differences (MID) in outcome measures. We also present 50% of the observed sample SD, a common rule-of-thumb for clinically meaningful differences.⁵⁹ The table shows that even with substantial shortfall in sample size (down to 65 per group) we still can detect differences below the estimated MID.

Detectable Outcome Differences with 80% Power						
Measure	SD	N= 75	N=70	N=65	ERES⁵⁸	.5 SD⁵⁹
Patient Activation Measure	13	3.4	3.5	3.6	8.0	6.5
Ostomy self-management self-efficacy	2.3	0.60	0.62	0.64	0.80	1.2
COH-QOL-CRC Total	1.6	0.42	0.43	0.45	0.88	0.8
COH-QOL-CRC Physical	1.8	0.47	0.49	0.51	0.88	0.9
COH-QOL-CRC Psychological	1.8	0.47	0.49	0.51	0.88	0.9
COH-QOL-CRC Social	2.1	0.55	0.57	0.59	0.88	1.1
COH-QOL-CRC Spiritual	2.2	0.57	0.59	0.62	0.88	1.1

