2.0 OBJECTIVES

2.1 Primary Objectives

Aim 1: Using our enhanced telehealth techniques, determine if **patient activation**, self-efficacy, ostomy-related knowledge, and HRQOL will be improved and sustained over time in the online interactive communication Ostomy Self-Management Telehealth program (OSMT) curriculum compared to a usual care (UC) group.

Hypothesis 1.1: Taking into account time since surgery:

- 1.1.1 Survivors in the OSMT group will have greater improvement in **patient activation** compared to UC.
- 1.1.2 Survivors in the OSMT group will have a sustained improvement in **patient activation**.
- 1.1.3 In survivors in the OSMT group, higher attendance levels will be associated with increased **patient activation**.

Hypothesis 1.2: Taking into account time since surgery:

- 1.2.1 Survivors in the OSMT group will have greater improvement in **self-efficacy, ostomy-related knowledge, and HRQOL** compared to UC.
- 1.2.2 Survivors in the OSMT group will have a sustained improvement in **self-efficacy, ostomy-related knowledge, and HRQOL**.
- 1.2.3 In survivors in the OSMT group, higher attendance levels will be associated with increased **self-efficacy, ostomy-related knowledge, and HRQOL**.

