12.0 STATISTICAL CONSIDERATIONS

12.1 General. Aim 1 will be analyzed with linear mixed models for repeated measures. Aim 2 will utilize a variety of sources and methods to enumerate the intervention program and ostomy-related family resources in each study arm.

If a subject misses Session 3 or Session 4 or both, they can make up the missed session(s) with the next 1 or 2 scheduled groups. If they miss both chances to make up the sessions, they

will be asked to do the surveys and will be analyzed as a separate group using an intent-to-treat contrast.

12.2 Aim 1: Using our enhanced telehealth techniques, determine if **patient activation**, self-efficacy, ostomy-related knowledge, and HRQOL will be improved and sustained over time in the online interactive communication Ostomy Self-Management Telehealth program (OSMT) curriculum compared to a UC group.

Under an intent-to-treat approach, change in outcomes will be evaluated longitudinally with linear mixed models, testing the effect of study arm adjusted for potential confounders. Such models evaluate both associations and rates of change, accounting for within-subject correlation. The Primary Outcome will be PAM. Secondary Outcomes include SE, COH-QOL-CRC scales, and Ostomy Knowledge. Post hoc contrasts will evaluate effect of training (baseline to post) and whether effect is sustained after training (6 month post to follow-up). Standard multivariable modeling procedures will be used to select or eliminate potential confounding variables, starting with candidate variables that are biologically plausible or found to be associated with endpoint change scores (baseline vs. follow-up) in bivariate analyses with a p-value of less than 0.20. Potential candidate covariates and confounders include (but are not limited to) CG participation in training sessions, depression (HADS), time since surgery, ostomy type, age, sex, stage, anticipated permanence of ostomy, and pre- or post-surgical radiation or chemotherapy. We will explore potential interaction for plausible effect modifiers, such as gender, or having a CG.

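### Section 12.2 and the SAP do not describe the baseline-adjusted, two-follow-up model on which the 80% power in 12.13 rests, and they label the contrast that tests Hypothesis 1.1.1 post hoc

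*Protocol*

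**What the plan says.** Hypothesis 1.1.1 (Protocol 2.1) concerns change relative to usual care: "Survivors in the OSMT group will have greater improvement in" patient activation.

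Protocol 12.2 and the SAP under Aim 1 carry the same sentence: "change in outcomes will be evaluated longitudinally with linear mixed models, testing the effect of study arm adjusted for potential confounders". The test itself is given only as "testing the effect of study arm adjusted for potential confounders". PAM is named as the primary outcome. The next relevant sentence is "Post hoc contrasts will evaluate effect of training (baseline to post"), followed by a second contrast for whether the effect is sustained. Neither document says whether baseline is a response or a covariate, whether the model has an arm-by-time term, or which contrast at which visit is primary. Baseline PAM is not among the candidate covariates, although that list is open-ended. Covariates are selected partly by bivariate screening at p < 0.20.

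Protocol 12.13 is more definite about the model behind the power figures: "Estimates are based on repeated measures multivariable modeling, adjusted for baseline", "with two follow-up measurements". Its assumptions are "1) alpha of 0.05, 2) within-subject correlation on repeated measures of 0.60". The table headed "Detectable Outcome Differences with 80% Power" gives, for PAM with SD 13, differences of 3.4, 3.5 and 3.6 points at 75, 70 and 65 per arm, beside benchmarks of 8.0 (ERES) and 6.5 (half an SD). The text adds 2.75 points for the larger sample. The SAP as provided has no power section.

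**The concern.** A baseline-to-post contrast taken from a mixed model needs baseline among the responses. A model adjusted for baseline with two follow-ups uses baseline as a covariate and has only two response occasions. Unless the baseline means are constrained to be equal across arms, these give different tests with different standard errors. An analyst working from 12.2 or the SAP alone could fit the less precise one and still be following the plan.

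Two things are at stake. The power stated for the primary outcome may not belong to the test that is reported. And because no contrast is named as primary, while the one that matches the primary hypothesis is called post hoc, a reader of the results could not confirm which PAM comparison was the confirmatory one.

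**Working it through.** **Inputs (Protocol 12.13).** SD 13; within-subject correlation ρ = 0.60; alpha 0.05; 80% power; 75 per arm; 3.4 points. **Assumptions.** Two-sided alpha (sidedness is not stated), equal arms, compound symmetry, the same effect at both follow-ups, and no true baseline difference.

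**Formulas.** SE = SD·√(2f/n), where f is the variance factor of the test. Power ≈ Φ(δ/SE − 1.96). Detectable difference = (1.960 + 0.842)·SE.

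**Reproducing the plan's figure.** With f = (1 − ρ²)/2 = (1 − 0.36)/2 = 0.32, the detectable difference at 75 per arm is 2.802 × 13 × √(0.64/75) = 3.36. At 70 and 65 per arm it is 3.48 and 3.61. These match 3.4, 3.5 and 3.6. The factor was found by matching the table. It treats the two follow-ups as uncorrelated once baseline is adjusted for. Under compound symmetry they are still correlated, so the like-for-like factor is (1 + ρ)/2 − ρ² = 0.80 − 0.36 = 0.44.

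**Tests that the wording could lead to, 75 per arm, 3.4 points**

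| Test | f | SE | δ/SE | Power | Detectable at 80% |
|---|---|---|---|---|---|
| 12.13's implied factor | 0.32 | 1.201 | 2.831 | 81% | 3.36 |
| Baseline-adjusted mean of two follow-ups | 0.44 | 1.408 | 2.414 | 68% | 3.94 |
| Baseline-adjusted, one follow-up, f = 1 − ρ² | 0.64 | 1.698 | 2.002 | 52% | 4.76 |
| Baseline-to-post change, f = 2(1 − ρ) | 0.80 | 1.899 | 1.791 | 43% | 5.32 |

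The last row applies when each arm has its own baseline mean. If the arms share one baseline mean, a contrast with baseline as a response recovers essentially the precision of the covariate-adjusted test.

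**Sensitivity to ρ from 0.4 to 0.8 (same n and δ).** Change contrast 31% to 72%; one adjusted follow-up 42% to 76%; adjusted mean of two 59% to 88%. The order does not change.

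**The larger sample.** If all 120 per arm completed, power at 2.75 points would be about 45%, 54% and 70% for the change contrast, one adjusted follow-up and the adjusted mean of two, against the stated 80%.

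**At the protocol's benchmarks, 75 per arm.** At 6.5 points: 93%, 97% and over 99%. At 8.0 points: 99% or more for all three (98.8%, 99.7% and over 99.9%).

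**The harshest reading.** For an arm effect averaged over baseline and both follow-ups, the effects 0, δ, δ average to 2δ/3 = 2.27. Here f = (1 + 2ρ)/3 = 0.733, SE = 1.818 and δ/SE = 1.247, so power is about 24%. At 6.5 and 8.0 points it is 66% and 83%.

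**The case against.** The best defence is that the documents, read together, already point to a baseline-adjusted comparison of change. The sentence in 12.2 begins with change in outcomes, the hypothesis is greater improvement, and 12.13 says the model adjusts for baseline. The covariate list is open, so baseline PAM is not excluded. The contrasts are written down in advance, and post hoc is often used loosely for contrasts that follow a model fit. The effects that the protocol treats as important are 6.5 and 8.0 points, where the choice of test costs little.

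Much of this stands, and it rules out two stronger readings. A reader might infer that the primary test is literally an arm main effect averaged over three visits, diluted by a third and left with about 24% power. No section describes such a test. The wording does not exclude it, but the references to change and improvement argue against it, and the availability of a baseline-to-post contrast does not make an averaged main effect the primary test. A reader might also infer that the confirmatory contrast is to be picked after seeing data. It is named in both documents beforehand; the label is poor wording, not evidence of data-driven choice.

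The defence does not settle which change is primary, at which visit, or how baseline enters. A sample-size section does not define the analysis, its model does not match the contrast in 12.2, and it does not appear in the SAP text provided.

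**Conclusion.** The point holds as a mismatch between the analysis and the power calculation. The contrast named in 12.2 and the SAP has about 43% power at the difference that 12.13 says is detectable with 80%, against about 68% for the test that 12.13 describes. The remaining gap from 68% to 80% comes from 12.13's variance factor, not from the analysis wording, and should not be charged to this point.

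These figures rest on two-sided 0.05, SD 13, ρ = 0.60, compound symmetry and arm-specific baseline means in the change contrast. The practical harm is limited to effects near the minimum detectable difference: even the change contrast can detect 5.32 points at 75 per arm, below both benchmarks. It is still worth correcting, because precision is given away for nothing and the primary test is left undefined.

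**What to change.** In 12.2 and the SAP, state that the primary test is one pre-specified, baseline-adjusted arm contrast in PAM. Fit arm, time and arm-by-time, with baseline PAM either as a covariate that is always in the model (not subject to the p < 0.20 screen) or as a response with a common mean across arms. Average the contrast over the end-of-sessions and 6-month visits, which matches the two follow-ups in 12.13. Keep the sustained-effect contrast as a separate, named comparison for Hypothesis 1.1.2.

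If the sponsor prefers a single visit, name it and restate the detectable difference for it: about 4.8 points at 75 per arm under the assumptions above. Remove the post hoc label from the contrast that tests Hypothesis 1.1.1, and repeat the model from 12.13 in the SAP.

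The cost is wording only. Baseline PAM is already collected (Protocol 8.2.1), and no visit, instrument or sample-size change is needed.

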7.2.2 Randomization

Patients who meet eligibility criteria will be approached to enroll in the randomized telehealth intervention versus a usual care comparison group using an approved consent process (see Schema). **Consents will need to be signed and received prior to randomization.**

Subjects will be randomized using stratified permuted block randomization. Once consented, the participant will be randomized to OSMT or UC, using computer-generated random lists blocked by site and gender, and with assigned arm in sealed envelopes blind to investigators and coordinators until assignment. This means that each participating site will have a unique pair of computer-generated randomization lists, one for male and the other for female, ensuring balance by sex between intervention and usual care groups at each site without the need for communication with a data coordinating center core for each randomization. The randomization lists will be comprised of blocks of 4 with permuted patterns so that balance is achieved after multiples of 4 in each sex have been randomized.

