8.1 Session Information/Preparation

Site coordinators at the three accrual sites will communicate to each other the number of subjects being assigned to a group as they are randomized to the Intervention arm. When the group enrollment gets to six, they will close enrollment to that group and begin enrolling in the next group. Coordinators will slow enrollment if needed so that subjects are not enrolled in a group starting more than 2 months from the enrollment date. If needed, the team will discuss adding additional groups to the schedule on different dates so that subjects will be able to start within the 2-month window from enrollment date.

For intervention session schedules, the protocol will include two different schedules for intervention session administration. This design is to provide flexibility for participants and also to maximize study accrual and participation. The schedules include:

Schedule #1: Two sessions administered on the same day, with a break in between. There will be a 4-week interval between the first set of 2 sessions and second set of 2 sessions. The caregiver session will be held two weeks after the first set of sessions.

Schedule #2: One session administered per day, once a week over a five-week period. There will be a one-week interval between session 2 and session 3 during which the caregiver session will be held.

The two schedules vary throughout the study period based on participants' convenience and preference.

If a subject misses a session, they can make up just the missed session with the next 1 or 2 scheduled groups rather than start over with a new group. If they miss both Session 1 and Session 2, they can be re-assigned to the next group as long as the next group size doesn't

exceed 6, or at the ostomy nurses' ([name] and [name]) discretion if the group size would exceed 6.

If a subject misses Session 3 or Session 4 or both, they can make up the missed session(s) with the next 1 or 2 scheduled groups. If they miss both chances to make up the sessions, they will be asked to do the surveys and will be analyzed as a separate group using an intent-to-treat contrast.

To account for making up sessions or delays in completing interim surveys, for both intervention and usual care groups, the 6-month followup surveys will be requested from subjects 6 months after the date the interim surveys are completed.

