9.0 STUDY PLAN

9.1 Usual Care

The UC control program is designed to compare OSMT to usual care to capture the Hawthorne effect. The final intervention for the UC group includes:

- 1) Recommending the patient has met at least once with an ostomy nurse (while likely to have happened in the peri-operative period, it may not be universal);
- 2) Providing the booklet published by The Wound, Ostomy, and Continence Nurses' Society entitled "Basic Ostomy Skin Care: A Guide for Patients and Health Care Providers," with instructions on how to use it;
- 3) Local support group contact information;
- 4) Encouraging patients to have seen their surgeons at least once in follow-up after surgery;
- 5) Contact information for local nutritional and physical therapists; and
- 6) Ostomy nurse contact information. If patients have specific questions about materials, the research coordinator will clarify the content and encourage the patient to call their physician or ostomy nurse about a continuing problem. These resources will also be given to those in the OSMT program.

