9.2.2 Ostomy Care Nurse-Facilitators. We have an experienced OCN-facilitator who will lead sessions from the Tucson site ([name]). She participated in the pilot study and is well-versed in the curriculum. Her back-up in Tucson ([name]) has also been instructed on the curriculum, Ostomy Care Nurse facilitators will train participants to become problem solvers, rather than simply giving them a health professional's solution. They will also participate in weekly research team meetings to give updates on issues and events as they transpire. In this way they will give feedback into what components of the program are problematic, as well as what aspects are working well (program evaluation). There will also be OCNs available at the

University of Pennsylvania (UP), City of Hope (COH) and Yale New Haven (YNH) sites as an added resource for participants.

9.2.3 Specific Ostomy Resource Compendium. We have compiled a Tucson-specific resource compendium to distribute to participants. This includes web-based, OCN resource lists, and personal knowledge to identify local ostomy resources, updated for UP, COH and YNH sites. (Appendix 12)

9.2.4 Program Curriculum. OSMT sessions are described in Table 5 below. The OSMT is organized around several concepts that provide the basis for the content and methods. The CCM points to the need for supporting self-efficacy enhancing, evidence based information and peer support. The CG literature points to the need for CGs to be able to step in and provide assistance when participants are unable to do for themselves, but not to take over totally and create dependency in their family member. The teaching content is divided into five 1.5 - 2 hour sessions: three solely for the participants, one for their CG, and one as a conjoined or single visit. Prior to Session 1, participants will list personal goals for participation in OSMT. Participants will be given an assignment at the completion of Session 2, which will be to monitor ostomy output (frequency and consistency of bowel movements and flatus), and problems related to pouching system. As urinary diversion patients also have interruption of their intestine to make their ostomy, with concomitant obstruction/stomal hernia risks, ostomy output issues may also be applicable to them. This exercise will assist the ostomate in becoming familiar with the relationships between input of food and drink, and ostomy output.

9.2.5 Preparation for sessions.

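### Aim 1 models ignore the OSMT session groups, so p-values and intervals are too optimistic if outcomes within a group are positively correlated

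*Protocol*

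**What the plan says.** Allocation is individual. Protocol 7.2.2 states: "Once consented, the participant will be randomized to OSMT or UC, using computer-generated random lists blocked by site and gender".

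Groups are formed after randomisation, and only from people allocated to OSMT. Protocol 8.1 states: "When the group enrollment gets to six, they will close enrollment to that group and begin enrolling in the next group". Membership and size are not rigid:

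- On reassignment: "If they miss both Session 1 and Session 2, they can be re-assigned to the next group". This applies while the next group stays within six, or at the ostomy nurses' "discretion if the group size would exceed 6".
- On the number of groups: "If needed, the team will discuss adding additional groups to the schedule on different dates".
- Single missed sessions can be made up with one of the next two groups.

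Members of a group share more than a timetable. Peers act as group buddies (9.2.1) and co-lead sessions (13.1.2). The content of Session 4 follows what the group asks for (table under 9.2.5), and its review section differs by cohort (Appendix 1). Usual care has no such structure: what follows "The final intervention for the UC group includes" in 9.1 is advice, a booklet and contact details.

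For the Aim 1 models, 12.2 and the SAP carry the same sentence: "Such models evaluate both associations and rates of change, accounting for within-subject correlation". The assumptions listed in 12.13 are alpha 0.05 and a within-subject correlation of 0.60. Session group is not a random effect, a cluster variable or a listed covariate. The separate group mentioned in 8.1 and 12.1 means people who miss their make-up sessions and does not deal with clustering.

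**The concern.** This is a partially nested design: one arm is clustered by delivery and the other is not. Individual randomisation makes the arms comparable at baseline. It does not remove correlation that arises afterwards from a shared group, shared peers and group-led content. A model that knows only about repeated measures treats OSMT participants as independent. If the within-group correlation is positive, it understates the variance of the OSMT mean.

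Two Aim 1 results are exposed: the between-arm effect (hypotheses 1.1.1 and 1.2.1) and the baseline-to-post contrast. The post-to-follow-up contrast (1.1.2 and 1.2.2) is not exposed if the group effect is the same at both post-baseline visits, because it then subtracts out. At stake are the p-values and confidence intervals for PAM, the primary outcome, and for self-efficacy, COH-QOL-CRC and ostomy knowledge.

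**Working it through.** **Inputs from the documents.** PAM SD 13, 75 completers per arm, within-subject correlation 0.60, alpha 0.05, 80% power, detectable PAM difference 3.4 (12.13); normal group cap of six (8.1); 23 calendar rows (10.0).

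**Assumptions.** ICC of 0.01 to 0.10 on the baseline-adjusted, time-averaged outcome; two-sided testing (12.13 does not state sidedness); 23 groups (8.1 allows more); site and gender are in the model or do not predict outcome.

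**1. The plan's own figure.** With variance factor (1 − 0.60²)/2 = 0.32:

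(1.96 + 0.84) × 13 × √0.32 × √(2/75) = 3.36, or 3.39 with t quantiles, which agrees with 3.4. It is obtained with no group correlation. The ratios below do not depend on this variance factor.

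**2. Between-arm effect.** Only the OSMT variance is inflated, by 1 + (m* − 1) × ICC, where m* = Σm_j²/n. Averaging with the unclustered arm gives

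- true SE / model SE = k = √(1 + (m* − 1) × ICC/2)
- type I error = 2 × (1 − Φ(1.96/k))
- power of an effect planned at 80% = Φ(2.80/k − 1.96)

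The most unequal split of 75 into 23 groups of 1 to 6 is ten groups of 6, one of 3 and twelve of 1: m* = (360 + 9 + 12)/75 = 5.08.

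| OSMT grouping | Type I, ICC 0.01 | ICC 0.05 | ICC 0.10 | Detectable PAM, ICC 0.10 |
|---|---|---|---|---|
| 75 in 23 equal groups (m* = 3.26) | 5.1% | 5.7% | 6.3% | 3.4 × 1.055 = 3.59 |
| 75 in 23, most unequal (m* = 5.08) | 5.2% | 6.2% | 7.4% | 3.4 × 1.097 = 3.73 |
| All groups of six | 5.3% | 6.5% | 8.0% | 3.4 × 1.118 = 3.80 |
| All groups of seven | 5.3% | 6.8% | 8.6% | 3.4 × 1.140 = 3.88 |

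At six per group, k is 1.012, 1.061 and 1.118, and power is 79%, 75% and 71%. At ICC 0.10, the 2.75-point PAM and 0.50-point self-efficacy differences in 12.13 become 2.75 × 1.118 = 3.07 and 0.50 × 1.118 = 0.56. Power at 6.5 PAM points is 99.8%.

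**3. Simulation** (20,000 replicates; 23 groups of 1-6 filled at random; 75 / 102 / 120 per arm). Type I error:

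| ICC | Groups ignored | OSMT-only group effect, Satterthwaite df |
|---|---|---|
| 0 | 4.8 / 5.0 / 5.0% | 4.2 / 4.3 / 4.4% |
| 0.01 | 5.1 / 5.4 / 5.5% | not run |
| 0.05 | 6.0 / 6.1 / 6.4% | 4.8 / 4.8 / 4.9% |
| 0.10 | 6.8 / 7.1 / 7.6% | 5.0 / 4.9 / 4.9% |

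**4. Contrasts.** If baseline-to-post is tested within OSMT, there is no unclustered arm to dilute the inflation, so the ratio is √(1 + (m − 1) × ICC). At six per group, with the ICC taken on the change score, type I error is 8.0% at 0.05 and 11.0% at 0.10. With the ICC defined on the baseline-adjusted average instead, simulation (78 in groups of six) gives 6.5% and 8.5%. Post-to-follow-up stays near 5% when the group effect is constant.

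**The case against.** The strongest reply is that the effect may be negligible. No document gives an ICC, and at 0.01 the error rate is barely above 5%. Several features hold the correlation down. Sessions are scripted, and 9.2.2 says "We have an experienced OCN-facilitator who will lead sessions from the Tucson site", with a back-up. Make-up sessions mix the groups. Seventy-five completers over 23 groups average 3.3 each, so the 8.0% and 8.6% figures need every group to be full. If site predicts outcome and is left out (12.2 lists sex but not site as a candidate covariate), the model SE is biased upward, which partly offsets the problem; that offset has not been sized. The proposed model is also slightly conservative at ICC 0 and estimates the ICC poorly.

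Most of this is fair, and it limits the size of the problem without removing it. The plan neither allows for the correlation nor says it is taken as zero, and the features above coexist with shared peers, possible leadership by other nurses (13.1.1) and group-led content.

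Three further points stand:

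- Section 12.2 does not say whether baseline-to-post is a within-OSMT or a between-arm contrast, and the inflation differs between the two.
- If the group effect fades by six months, post-to-follow-up is affected too, and one intercept shared by both visits would not correct that.
- Section 8.1 has coordinators exchanging numbers per group and 9.4 uses first names, so the link from group to study ID should be confirmed.

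**Conclusion.** The concern holds on its conditional terms. If outcomes within OSMT groups are positively correlated, the planned models understate the SE of the between-arm effect and the baseline-to-post contrast. For the between-arm test the likely size is modest: type I error of 5.1-6.8% with 75 OSMT completers in 23 unequal groups, and up to 8.0% at six per group, over an assumed ICC of 0.01 to 0.10. At an ICC of zero there is no effect. A larger ICC or larger groups would make it worse. The sample size conclusion in 12.13 is unaffected: 3.8 points at six per group and ICC 0.10 is still well below 6.5. The change should be made because it protects inference on the primary outcome at little cost. Confidence is medium because the ICC is unknown.

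**What to change.** In 12.2 and the SAP:

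- Add a random intercept for session group in the OSMT arm only, acting on both post-baseline visits, with each usual care participant a singleton.
- Allow arm-specific residual variance, so that group variance is not confused with a difference in residual variance between arms.
- Use Kenward-Roger or Satterthwaite degrees of freedom.
- Define one group per OSMT participant: the group in which training began, after any reassignment under 8.1. Make-up sessions do not change it. Those who attend no session are singletons.
- Repeat with the group first assigned at randomisation as a sensitivity analysis. Group sets only the correlation structure; everyone stays in the randomised arm.
- If the group variance is estimated as zero, keep and report that fit.
- Report the ICC with its confidence interval, describe it as imprecise, and note that influence from peers who work across groups is not captured.

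In 12.13, state that the power and detectable differences assume an ICC of zero.

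The cost is mainly wording. Group assignment (8.1) and attendance (9.4) are already part of trial conduct, subject to confirming the link to study ID. Intervals become slightly wider: at ICC 0, simulated power falls from about 80% to 78% and type I error is 4.2-4.4%. At a true ICC of 0.05 the estimated ICC has an SD of 0.06-0.08, and the group variance is estimated as zero in 26-36% of trials.
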